1. LIST OF ABBREVIATIONS

Acronym	Title
AE	adverse event
CRF	case report form
CRP	C-reactive protein
EDP	exposure during pregnancy
ID	identification
IEC	independent ethics committee
IRB	institutional review board
MHLW	Ministry of Health, Labour and Welfare
MIC	minimum inhibitory concentration
N/A	not applicable
NIS	non-interventional study
PID	pelvic inflammatory disease and other related diseases
PMDA	Pharmaceuticals and Medical Devices Agency
RMP	Risk Management Plan
SAE	serious adverse event
SAP	statistical analysis plan
SRSD	Single Reference Safety Document
WBC	white blood cell

3. AMENDMENTS AND UPDATES

Amendment number	Date	Substantial or administrative amendment	Protocol section(s) changed	Summary of amendment(s)	Reason
Amended1	10 January 2017	Other amendment(s)	4. 7.2.4.	Section 4. Change in the end of data collection from "March 2017" to "May 2017" Section 7.2.4. Change in investigation period from "April 2015 to March 2017" to "April 2015 to May 2017" and change in registration period from "April 2015 to January 2017" to "April 2015 to March 2017"	It was decided to extend investigation period and registration period another 2 months, since it is possible that the target number of patients in the safety analysis set would not be reached by the end of the registration period planned in this study.

4. MILESTONES

Milestone	Planned date
Start of data collection	April 2015
End of data collection	May 2017
Final study report	To be decided

5. RATIONALE AND BACKGROUND

Anaemetron I.V. Infusion 500 mg (hereinafter referred to as "this drug") is an injection of metronidazole, which has been used for a long time in Japan. Metronidazole has a strong antibacterial or antiprotozoan activity against obligate anaerobes or protozoa respectively; for which, it is recommended in various domestic and overseas guidelines and textbooks, and highly regarded as a therapeutic method for anaerobic infection.

Anaerobic infection developed in patients with severe underlying diseases frequently becomes more refractory or serious due to the patients' susceptibility to infection. Patients in such a serious condition often have difficulties taking oral medications, and thus, metronidazole injection would be beneficial.

Such background warrants the great clinical significance to make metronidazole injection clinically available; for which, Pfizer obtained the approval to manufacture and market this drug in Japan in July 2014.

The drug use investigation of Anaemetron I.V. Infusion 500 mg (hereinafter referred to as "this study") shall be conducted to collect information regarding the occurrence by type of adverse reactions associated with this drug in daily clinical practice, and information regarding the quality, effectiveness, and safety of this drug. The information collected from this study shall be used to provide proper use information and prepare documents for the application of re-examination.

This study shall be conducted in strict compliance with the "MHLW Ordinance on the Standard for Post-Marketing Studies and Clinical Trials of Medical Products" (MHLW Ordinance No. 171 dated December 20, 2004).

Data obtained from the patients registered in this study will be reported to the MHLW pursuant to the Pharmaceutical and Medical Device Act; pertinent to which, data may be publicly posted in MHLW's "Pharmaceuticals and Medical Devices Safety Information" and "Pharmaceuticals and Medical Devices Information Website" (<http://www.info.pmda.go.jp>) as a listing of patients, which will present the names of drugs, adverse reactions, sex, age (increment of 10 years), and other relevant information. Furthermore, data collected may also be disclosed if the MHLW is required to disclose such information in accordance with the "Act on Access to Information Held by Administrative Organs" (Law No. 42 dated May 14, 1999) provided that in no event will the names of physicians, medical institutions, and other personal information be subject to such disclosure, nor will it be posted or disclosed in any form or shape.

6. RESEARCH QUESTION AND OBJECTIVES

This study will be conducted to investigate the safety and effectiveness of this drug in daily clinical practice. Additionally, it is intended to assess the following:

- Adverse reactions unexpected from precautions, and
- Occurrence of adverse reactions under actual clinical settings

"Central nervous system disorder" also will be confirmed for the tendency of adverse reactions under actual clinical settings.

6.1. Safety specifications

[Important Identified Risks] Central nervous system disorder

7. RESEARCH METHODS

7.1. Study design

This study is a multicenter open-label study conducted in patients receiving this drug; for which, case report forms (CRFs) will be recorded based on data presented in medical records obtained in daily clinical practice.

7.2. Setting

Patients who satisfy all of the inclusion criteria are subject to this study.

7.2.1. Inclusion criteria

Patients who have not used metronidazole (injection) in the past, and have been administered this drug for treatment of anaerobic infection, infectious enterocolitis, or amebic dysentery. Patients who have used metronidazole (oral agent and vaginal tablet) in the past are eligible, and should not be excluded from this study.

7.2.2. Exclusion criteria

No exclusion criteria are set out in this study.

7.2.3. Sites for this study

The sites with presence of doctors specialized in the target therapeutic area primarily in the following departments, at which, this drug can be prescribed:
Gastroenterology, gastroenterological surgery, respiratory medicine, gynecology, and infection

7.2.4. Planned investigation period

Investigation period: April 2015 to May 2017

Registration period: April 2015 to March 2017

(Even before the end of the registration period, registration will be discontinued if the target number of patients is reached)

7.2.5. Study methods

This study will be a prospective study, in which, patients will be registered with central registration system until the target number of patients meeting the registration criteria are reached.

7.2.6. Observation period

The observation period shall start on the day the treatment with this drug begins and end on the day the treatment is completed; however, it shall be cut off at Week 8 after the initiation of treatment (Day 56 counting from Day 1 as the day the treatment begins) if the treatment is prolonged.

7.3. Variables

This study will be conducted in accordance with the following variables/schedule of observation (Table 1).

Table 1. Variables/schedule of observation

Variables	Timing	Initiation of treatment	Observation period	Completion of observation period
Background	ID number	●		
	Sex	●		
	Age (on the date of treatment initiation)	●		
	Height/body weight	●		
	Hospitalization status (inpatient/outpatient)	●		
	Targeted disease	●		
	Medical history	●		
Targeted drug use record		●		
Concomitant therapy (Drug therapy)		●		
Vital sign/laboratory tests (body temperature, WBC count, and CRP)			●	
Microbiological test			●	
Effectiveness evaluation				●
End-of-study (discontinuation) record				●
Adverse events			●	

●: Data items to complete

7.3.1. Background

Input the information at the initiation of treatment with this drug.

- [1] ID number
- [2] Sex
- [3] Age
- [4] Height
- [5] Body weight
- [6] Hospitalization status (inpatient/outpatient)
- [7] Targeted disease (infection for which this drug is used)
 - Name of disease
 - Severity
- [8] Medical history (information except for targeted disease)
 - Presence/absence of hepatic functional impairment or renal functional impairment

- Name of disease or syndrome other than the above, as well as the history or the complication
- [9] History of surgery if the targeted disease is a secondary infection due to surgery
- Disease name for which the surgical operation is performed
 - Date of surgery

7.3.2. Targeted drug use record

The following will be recorded for the targeted drug.

- [1] Daily dose
- [2] Number of doses per day
- [3] Treatment period (start date/end date)
- [4] Reason for change of dose

7.3.3. Concomitant therapy

7.3.3.1. Drug therapy

Medications used for the infection

The following information will be recorded for medications used for the infection during a period from 14 days before the initiation of treatment with this drug to the completion date of observation period.

- [1] Drug name (product name)
- [2] Route of administration
- [3] Date of treatment initiation
- [4] Presence/absence of concomitant use at the time the treatment with this drug begins

7.3.4. Tests

7.3.4.1. Vital sign/laboratory tests

Vital sign/laboratory tests

Record the following vital sign/laboratory parameters before the initiation of treatment with this drug, during the observation period, and at the completion of observation period.

[Vital sign/laboratory parameters] Body temperature, WBC count, and CRP

- Test date

- Test results

7.3.4.2. Other tests

Microbiological test

Record the pathogen for which this drug is used, and the expected results of test on the causative organism. Record the following information before the initiation of treatment with this drug, during the observation period, and at the completion of observation period.

- [1] Specimen
- [2] Pathogen, and the name of causative bacterial strain
- [3] Date of sampling
- [4] Test method
- [5] Pathogen result (Semi-quantitative) (-, +, ++, +++, Unknown)
- [6] MIC of this drug
- [7] Presence/absence of ameba protozoa

7.3.5. End-of-study (discontinuation) record

If the observation is completed or discontinued before the end of the longest observation period (8 weeks), the reason should be recorded.

If an adverse event (AE) is selected for the reason, the information in details should be recorded in the AE column.

[Reason for completion]

- Cured (effective)

[Reason for discontinuation]

- Insufficient clinical response
- AE
- Hospital transfer
- Others

Presence/absence of pregnancy on the completion date of the observation period (if present, the delivery date or expected date of delivery)

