7.3.6. Effectiveness evaluation

(1) Clinical response

The clinical response of this drug should be evaluated comprehensively at the completion of the observation period, and the results should be recorded.

If this drug is administered continuously for more than 8 weeks, the clinical response should be evaluated comprehensively at Week 8.

- Effective
- Not effective
- Indeterminate (the reason should be recorded.)

The assessment criteria shall be as follows:

Table 2. Assessment criteria for [anaerobic infection] / [infectious enterocolitis (including pseudomembranous colitis)]

Assessment	Definition
Effective	Clinical symptoms accompanying the infection observed at the initiation of treatment with this drug has improved at the time of assessment, and treatment with other antibacterial drugs after the time of assessment is determined not necessary.
Not effective	"Effective" criteria are not met.
Indeterminate	Clinical response is difficult to evaluate.

Table 3. Assessment criteria for [amebic dysentery]

Assessment	Definition
Effective	Clinical symptoms accompanying the infection observed at the initiation of treatment with this drug has improved at the time of assessment, and treatment with other antibacterial drugs other than antiamebic agents (paromomycin, etc.) after the time of assessment is determined not necessary.
Not effective	"Effective" criteria are not met.
Indeterminate	Clinical response is difficult to evaluate.

Any clinically problematic finding compared to the initiation of treatment should be recorded in details in the AE column.

(2) Rationale for clinical response assessment

The rationale for the clinical response assessment ("Effective" or "Not effective"), on the disease for which this drug is used, should be recorded.

[Anaerobic infection]

General clinical findings, body temperature, WBC count, CRP level, imaging, and others

[Infectious enterocolitis (including pseudomembranous colitis)]

General clinical findings, Clostridium difficile TOXIN test, frequency of diarrhea, body temperature, abdominal pain, and others

[Amebic dysentery]

General clinical findings, ameba test, frequency of diarrhea, body temperature, abdominal pain, and others

(3) Microbiological response assessment

Microbiological response at the completion of observation period compared to prior to the initiation of treatment with this drug should be assessed, and the results should be recorded.

Table 4. Assessment criteria for microbiological response

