8.2. Statistical Analysis

8.2.1. Overview of Patients

- Number of sites by establisher and number of patients**

In completed patients, the number and proportion of sites by establisher shown below and the number and proportion of patients will be calculated.

- University hospitals
- National hospitals established by the Ministry of Health, Labour and Welfare
- Prefectural and municipal hospitals
- Public organizations
- Hospitals other than the above four established by corporations and individuals
- General practitioners/clinics

In addition, the mean, minimum, and maximum will be calculated for the number of patients per site.

- Dispositions of patients**

In patients who registered to the Study, the number of registered patients, the number of completed patients, the number of patients included in the analysis of safety, the number of patients included in the analysis of clinical response, and the number of patients included in the analysis of microbiological response will be tabulated. In addition, the number of no-CRF-collected patients, the number of patients excluded from the analysis of safety, clinical response, and microbiological response and the number of patients by reason for exclusion will be tabulated.

- Listing of discontinuations and dropouts**

In the safety analysis set, clinical response analysis set, and microbiological response analysis set, the number and proportion of discontinued patients per discontinuation time [<3

days, ≥ 4 to ≤ 7 days, ≥ 8 to ≤ 14 days, ≥ 15 to ≤ 21 days, ≥ 22 days] will be tabulated. In addition, the number and proportion of patients by reason for discontinuation will be tabulated.

- **Listing of excluded patients**

The listing of reasons for exclusion in patients excluded from the analysis of safety and clinical response will be prepared.

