8.2.2. Patient Background and Treatment History of Anametro

- **Patient background**

In the safety analysis set, clinical response analysis set, and microbiological response analysis set, the following patient background factors will be tabulated in accordance with Section 8.1.

- Sex [male, female]
- Age (continuous)
- Age group [<15 years, ≥ 15 to <65 years, ≥ 65 years]
- Age group [≥ 10 to <20 years, ≥ 20 to <40 years, ≥ 40 to <65 years, ≥ 65 to <70 years, ≥ 70 to <75 years, ≥ 75 years]
- Inpatient/outpatient status at the first prescription [inpatient, outpatient]
- Body weight (continuous)
- Body Mass Index (continuous)
- Diagnostic name* (anaerobic infection, infectious enterocolitis, amebic dysentery, others)
- Detailed diagnosis name of anaerobic infection
- Severity [mild, moderate, severe, unknown]
- Hepatic dysfunction [absent, present]
- Renal dysfunction [absent, present]
- Past medical history other than hepatic/renal dysfunction [absent, present]
- Concurrent illness other than hepatic/renal dysfunction [absent, present]
- Prior treatment (medication for infection) [absent, present]
- Concomitant medication (medication for infection) [absent, present]

* The same patient may have multiple diagnoses. In such case, additional categories may be added (e.g., anaerobic infection plus infectious enterocolitis).

In addition, patient background will also be tabulated by maximum number of daily doses and by the presence or absence of a central nervous system disorder.

In the safety analysis set, the number and proportion of the following patients will be tabulated by SOCs and PTs of MedDRA.

- Past medical history other than hepatic/renal dysfunction

- Concurrent illness other than hepatic/renal dysfunction.

In the safety analysis set and clinical response analysis set, the number and proportion of the following patients will be tabulated.

- Presence or absence of pregnancy
- Concomitant medication (medication for infection)
- Prior treatment (medication for infection)

- **Status of treatment of Anaemetro**

In the safety analysis set, the following status of treatment of Anaemetro will be tabulated:

- Duration of treatment (continuous)
- Duration of treatment (1) [1, 2, 3, 4, 5, 6, 7, 8, 9, 10, 11, 12, 13, 14, 15, 16, 17, 18, 19, 20, 21, ≥ 22 days]
- Duration of treatment (2) [≤ 3 day, ≥ 4 to ≤ 7 days, ≥ 8 to ≤ 14 days, ≥ 15 to ≤ 21 days, ≥ 22 days]
- Duration of treatment (3) [≤ 3 days, ≥ 4 to ≤ 10 days, > 10 days]

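### Protocol 7.3.5 lists no completion code for a course finished before Week 8 without an Effective rating, and the SAP 8.2.1 discontinuation bands leave out day 3

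*Protocol*

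**What the plan says.** Protocol 7.3.5 sets the rule for the end-of-study record: "If the observation is completed or discontinued before the end of the longest observation period (8 weeks), the reason should be recorded". Under the completion heading it lists one reason, "Cured (effective". Under the discontinuation heading it lists four: "Insufficient clinical response", adverse event, transfer to another hospital, and a catch-all for others.

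Protocol 7.2.6 defines the end of observation by treatment and not by outcome: "The observation period shall start on the day the treatment with this drug begins and end on the day the treatment is completed", with a cut-off at Day 56. Protocol 7.3.6 then asks for a rating at that point: "The clinical response of this drug should be evaluated comprehensively at the completion of the observation period, and the results should be recorded". The rating may be Effective, Not effective or Indeterminate.

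SAP 8.2.1 plans, for the safety, clinical response and microbiological response sets, "the number and proportion of discontinued patients per discontinuation time [<3" days, followed by 4–7, 8–14, 15–21 and ≥22 days. It also plans a table by reason for discontinuation. The matching bands for treatment duration in SAP 8.2.2 begin differently: "Duration of treatment (2) [≤ 3 day, ≥ 4 to ≤ 7 days", and then continue identically.

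**The concern.** The end-of-study record mixes two things: whether treatment ran to its end, and whether it worked. The only completion reason is an outcome, so a course that ended without that outcome has nowhere to go except under discontinuation. If SAP 8.2.1 counts those records as they stand, its discontinuation proportion combines early stops with finished but unsuccessful or unratable courses. A reader of the re-examination report would probably take it as early stopping alone.

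The time bands raise a separate, mechanical problem. A patient who discontinued on day 3 belongs to none of them, so the missing patients would all be very early stops.

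**Working it through.** **Plan's own figure.** The plan states no expected discontinuation or response rate, so there is no figure on this point to reproduce. Its one design figure (Protocol 7.5.2: 100 patients, 3% incidence, 95% probability) is sound, since 1 − 0.97^100 = 0.952, and it is not affected by this point.

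**Step 1: the listed codes against the possible ratings** (Protocol 7.2.6, 7.3.5, 7.3.6).

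| How observation ended | Rating | Completion code listed? | Where the record can go |
|---|---|---|---|
| Treatment finished before Week 8 | Effective | Yes | Completion |
| Treatment finished before Week 8 | Not effective | No | Discontinuation: insufficient response or others |
| Treatment finished before Week 8 | Indeterminate | No | Discontinuation: others |
| Stopped for adverse event or transfer | Any | Not needed | Its own discontinuation code |
| Still on treatment at Day 56 | Any | Not needed | No reason required |

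The second row includes some patients who improved. Under Protocol Table 2, Effective also requires that "treatment with other antibacterial drugs after the time of assessment is determined not necessary", and Table 3 has the same condition with an exception for antiamebic agents. A patient who improved but goes on to another antibacterial drug is therefore Not effective and has no completion code. A patient who improved and needs nothing further is Effective and does have one.

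**Step 2: what the SAP does with the codes.** SAP 8.2.1 does not define discontinued and gives no rule to separate rows 2 and 3 from genuine early stops. It also refers to completed patients without defining them, so that term does not settle the matter.

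**Step 3: the time bands.** Assign each day from 1 to 56 to a band.

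- SAP 8.2.1 as printed: days 1–2, 4–7, 8–14, 15–21 and 22–56 hold 2 + 4 + 7 + 7 + 35 = 55 days. Day 3, and only day 3, has no band.
- With the first band as in SAP 8.2.2: 3 + 4 + 7 + 7 + 35 = 56 days, each in exactly one band.

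The time-to-adverse-reaction table in SAP 8.2.3.1 also starts at ≤3 days.

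**Step 4: possible size of the inflation (all inputs assumed).** Let t be the share who truly stop early, and q the share who finish before Week 8 without an Effective rating. If all of q is filed under discontinuation, the tabulated proportion is t + q.

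| t | q = 5% | q = 10% | q = 20% | q = 30% |
|---|---|---|---|---|
| 5% | 10% | 15% | 25% | 35% |
| 10% | 15% | 20% | 30% | 40% |
| 20% | 25% | 30% | 40% | 50% |

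**Step 5: possible number without a time band (all inputs assumed).** With D discontinued patients and a share s of them stopping on day 3, the expected number unassigned is D × s, and the chance of at least one is 1 − (1 − s)^D.

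| D | s | Expected | Chance of at least one |
|---|---|---|---|
| 5 | 5% / 10% / 20% | 0.25 / 0.5 / 1 | 23% / 41% / 67% |
| 20 | 5% / 10% / 20% | 1 / 2 / 4 | 64% / 88% / 99% |

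**The case against.** The strongest reply has five parts.

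- **The blank CRF is not in the documents.** Protocol 7.3.5 is an item list, and the SAP shows that the form has options the protocol does not list, such as an others box for the disease (SAP 5.2.1). Miscoding is therefore an inference from the code list. This stands, and it is why the conclusion is that the proportion may be inflated, not that it is.
- **Filing an end of treatment without effect under discontinuation is a defensible convention.** The protocol records no planned course length (7.3.2), and stopping for insufficient response is a genuine discontinuation. This stands for part of the Not effective group. It does not cover Indeterminate ratings, and the SAP does not state the convention.
- **The band gap looks like a slip for ≤3.** That is likely, because the other four bands match SAP 8.2.2. A reading error from the PDF cannot be fully excluded, although ≤ prints correctly elsewhere in the same bracket. SAP 8.2.2 does show day-3 treatment durations, but for the whole safety set, so it does not recover the day-3 discontinuations. No patient leaves the overall count or the table by reason.
- **It is too late to change the form.** This stands: data collection was planned to end in May 2017 (Protocol 4), and the last SAP entry has database release in preparation.
- **Recoding may not reach everyone.** Protocol 7.3.5 does not say that free text is collected with the catch-all reason, and patients coded as insufficient response would not be reached through it. This also stands.

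A reader might go further and infer that the discontinuation proportion is roughly the complement of the response rate, for example 15 to 20% if response were 80 to 85%. The documents do not support that. They give no such response rate, and the response denominator excludes Indeterminate ratings (Protocol 7.7). Effective patients can still stop for an adverse event or transfer, patients treated to Day 56 need no code, and some Not effective patients did stop early.

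A reader might also infer that the table says nothing about tolerability. That does not follow either. Adverse event is its own reason row, and SAP 8.2.3.1 tabulates adverse reactions by intervention, including discontinuation.

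**Conclusion.** The point holds on two counts, both confined to the SAP 8.2.1 discontinuation table.

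1. **Coding.** As listed, finished courses rated Not effective or Indeterminate before Week 8 have no completion code. The discontinuation proportion may therefore be inflated by an amount that the documents do not allow to be computed. The ranges in steps 4 and 5 of the working rest wholly on assumed shares and show sensitivity only. Step 4 also assumes that every such course is filed under discontinuation.
2. **Bands.** As printed, day 3 falls in no band, so the time table need not sum to its total. This follows from the text alone and needs no assumption beyond its being correctly read from the PDF.

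Neither count supports calling the whole table wrong. Clinical response is recorded separately under Protocol 7.3.6, so the clinical response rate, the eradication rate and the adverse-reaction incidences are unaffected.

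**What to change.** - In SAP 8.2.1, change the first band to ≤3 days so that it agrees with SAP 8.2.2. This is a one-symbol change.
- Before database release, define discontinued in SAP 8.2.1 so that finished courses without an Effective rating appear on a separate line from early stops. Use the recorded reason, the treatment dates and the Protocol 7.3.6 rating. Section 7.3.6 also collects the reason for an Indeterminate rating and the rationale for the other two, which should help.
- Where these data cannot separate the two groups, footnote the table to say that discontinuation includes finished courses not rated cured.

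The cost is a short SAP revision and some recoding. No new patient data are needed. Because no planned course length is recorded, some patients may stay unclassifiable, and the footnote covers them.
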